5.0 Inclusion and Exclusion Criteria/ Study Population

Inclusion Criteria: 1. Adult volunteers over the age of 18 who are able to provide written informed consent in English or Spanish; 2. Current hospitalization with a suspected, or known bacterial or viral (HIV/HCV/HBV) infection including but not limited to bacteremia, Candidal fungemia, osteomyelitis, endophthalmitis, septic thrombophlebitis, infected pseudoaneurysm, community acquired pneumonia, endocarditis, skin/soft tissue infection (SSTI), or septic arthritis; 3. Current moderate-to-severe OUD (DSM-5); 4. Willing to accept assignment to either ID/LAB or TAU, and to participate in research follow-up visits. Exclusions: 1. Severe medical or psychiatric disability making participation unsafe (e.g. imminent suicide risk); 2. Pregnancy, planning conception, or breast-feeding for female participants; 3. Allergy, hypersensitivity or medical contraindication to buprenorphine; 4. Moderate-severe liver impairment in the judgment of the study investigator; 5. Preexisting enrollment on methadone or buprenorphine (SL-B) maintenance AND intending to remain on methadone or buprenorphine maintenance upon discharge (patients already under effective treatment for OUD do not represent the target population of untreated OUD patients entering hospitals, nor would we want to disrupt established effective treatment). 6. Inability or unwillingness of subject to give informed consent.

A screening form that includes chart review and assessment of the above inclusion and exclusion criteria will be used to identify eligibility for the study. This form is located in the appendix.

Eligibility Screening:

The study team at each Site will conduct regular outreach to the staffs of these services to make them aware of the study and how to refer patients, and work with the attending physician to determine likely eligibility. In many cases, potentially eligible patients will be admitted to the ID or Hospitalist service that is conducting the study. Research assistants will conduct a daily chart review of the patient lists for the Infectious Diseases and Hospitalist teams via the electronic medical record to pre-screen for eligibility. In addition, informational study flyers will be distributed to the Infectious Disease, Addiction Medicine (if applicable) and hospitalist teams with the contact information of the project coordinator for referral of participants or can contact the study team via electronic health record (EPIC) Inbox messaging. Potential participants will be asked if they would like to meet with our study staff. They will be reassured that involvement or non-involvement in the study will not have any bearing on their treatment or hospital stay. All potential participants will be screened in a confidential setting using the computer-assisted interview program.

The Gender and Minority breakdown will vary per study site. These proportions are consistent with the clinical population of opioid users in each region. It is estimated that the sample for our principle recruiting sites will be:

- Hershey, PA: 60% Male, 91% Caucasian, 2% Black or African-American, 4.8% Asian, and 1.4% more than one race; Ethnically 1.5% Hispanic or Latino
- Greenville, SC: 70% Male, 67% Caucasian, 9% Black or African-American, 3% Asian, and 10% more than one Race; Ethnically 7% Hispanic or Latino.
- New Haven, CT: 70% Male, 73% Caucasian, 20% Black or African-American, and 7% Other or More than one Race, Ethnically 27% Hispanic or Latino.

Children will not be included in this study.

6.0 **Number of Subjects**

N = 200 total (N = 100 per study arm), approximately 67 per site-region.

7.0 **Setting**

Patients eligible for the study will typically be admitted either through the emergency department or directly to the medical wards. The study team at each Site will conduct regular outreach to the staffs of these services to make them aware of the study and how to refer patients, and work with the attending physician to determine likely eligibility. In many cases, potentially eligible patients will be admitted to the ID or Hospitalist service that is conducting the study.

Yale New Haven Hospital sites:

The 944-bed Yale-New Haven Hospital (YNHH), encompassing the York Street and St Raphael campuses in New Haven, CT, serves this medium sized city and its surrounding suburban towns as well as being a tertiary care referral center for the southern New England region. The New Haven hospitals noted above will act as the primary recruiting sites in Connecticut. Bridgeport Hospital, also a member of the YNHH health system, is a 501-bed hospital which serves the southwestern region of the state, and will be a recruiting sub-site, led by [name]. [name] is an internal medicine physician, with addiction medicine experience, sees hospitalized patients and outpatients through the Primary Care Center in Bridgeport. All of these participating hospitals are heavily affected by the opioid epidemic. The Infectious Diseases Section of the Department of Internal Medicine, based at YNHH, is comprised of 36 full-time Faculty, including MPI [name], who will lead the research team there, and 5 others with a Waiver to prescribe buprenorphine. The ID service sees over 200 consultations every month at the York Street and St. Raphael campuses in fiscal year 2017, including 8.5/month MSSA and 14.3/month MRSA bacteremia, often IDU related. The YNHH ID service itself does not have a current standard care for persons with OUD. There is

a newly established Addiction Medicine consult team that is available at YNHH. 'Treatment as usual' ranges from Addiction medicine consultation with possible initiation onto MOUD, to no Addiction consultation followed by detoxification from opioids while inpatient.

St. Mary's Hospital:

Saint Mary's Hospital, owned by Trinity Health of New England is a 347-bed hospital located in Waterbury, Connecticut, in the Naugatuck Valley. This region has been impacted greatly by the opioid epidemic, including associated opioid-related hospitalizations and infections. [name] is an infectious disease specialist with expertise in HIV and HCV disease management and will be the local site investigator. He sees patients both in the hospital and in his outpatient clinic. Current standard care for the OUD for these patients consists of detoxification and referrals for outpatient treatment after hospital discharge.

Columbia and Mid Atlantic site:

The Penn State Health Milton S. Hershey Medical Center is a 548-bed level I Trauma hospital and the primary academic teaching site for the Penn State College of Medicine. The medical center serves a catchment area that includes the town of Hershey, nearby Harrisburg, and the general region of rural Southeastern Pennsylvania. As elsewhere across the rural U.S., these areas have seen a substantial increase in OUD in recent years. [name], an ID specialist, will lead the research team there in collaboration with the CTSA/CTN research team at Columbia ([name] and colleagues). Current standard care for the OUD for these patients consists of detoxification and referrals for outpatient treatment after hospital discharge.

MUSC and SC site:

Prisma Health includes the main safety net hospital (Greenville Memorial Hospital, GMH) and is the main healthcare resource for the 11-county upstate region of South Carolina and beyond, a largely rural area including counties such as Greenville, Pickens, Oconee, and Anderson, that have been particularly hard hit by the OUD epidemic. [name], a General Internist, Professor and Vice Chair in the Department of Medicine at South Carolina School of Medicine and Prisma Health, who has a career focus on co-occurring OUD and HCV, will lead the study at GMH in collaboration with the CTSA/CTN research team at MUSC ([name] and colleagues). In 2017, GMH admitted over 5,000 patients with severe infections, often OUD-related, managed by ID specialists and hospitalists. Current standard care for OUD is detoxification and consultation with a social worker who provides referral for care after discharge either to the Phoenix Center, a local addiction treatment program that offers SL-Bup maintenance, or Prisma Health Recovery Program.

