Secondary outcomes: 1) Days using opioids, and days injecting drugs per 28 days prior to each major assessment point (weeks 4, 8, 12, and 24 post randomization) (longitudinal, continuous); 2) Urine toxicology-confirmed abstinent (urine toxicology negative for illicit opioids, and self-report negative over past 7 (at week 1) or 30 days (weeks 4, 8, 12, 24) (longitudinal, binary); 3) Completion of the prescribed course of antimicrobial therapy (binary), Re-hospitalization for infection by week 12 (binary); 4) Days using other drugs/alcohol per 28 days prior to each assessment (longitudinal, continuous); 5) Urine toxicology positive for non-opioid drugs (longitudinal, binary); 6) Social functioning and quality of life (WHOQOL-Bref) at 12 and 24 weeks after randomization (longitudinal, continuous); 7) Modified PEG Pain Scale at each assessment (Longitudinal, continuous) 8) HIV risk behaviors—days in past 28 days of vaginal or anal sex without a condom at weeks 4, 8, 12, 24 (longitudinal, continuous); 8) Any needle sharing in past 28 days (longitudinal, binary); 9) Treatment satisfaction (via the TSR)¹² at 12 and 24 weeks (longitudinal, continuous); 10) Discharge “against medical advice” (binary); 11) Cure of index infection (binary); 12) HCV cure or link to treatment (binary); 13) HIV Viral suppression (Viral Load < 200 copies), if HIV positive (binary); 14) overall hospitalization by week 12; 15) ED visits by week 12; 16) Serious adverse events (SAFETEE and non-fatal and fatal overdose) (binary).

Additional variables: *Covariates, primary and secondary analyses: Stratification factors:* Site (3 sites: YNHH; Columbia/Penn State Hershey; South Carolina/Greenville) will be included as a fixed effect in all analyses. *Covariates:* In general, the baseline score for each outcome measure (where applicable) will be included as a covariate in outcome analyses. *Moderators:* A range of baseline moderator variables will be explored including 1) Demographic characteristics (gender, age, ethnicity, living situation (domiciled vs homeless); 2) Modified Pain PEG scores at baseline (continuous) 3) Evidence of fentanyl use at admission (urine toxicology, self-report) (binary); 4) Other substance use at baseline (any cannabis, any stimulant, any heavy drinking days; binary); 5) Probable major depression at baseline (binary based on PHQ score); 5) Type of infection (endocarditis/ osteomyelitis/bacteremia/ cellulitis/ etc.). *Mediators:* 1) Social functioning

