Secondary outcomes: Statistical Models: For each of the secondary outcomes (see above) the effect of randomization to the ID/LAB arm compared to the TAU arm will be estimated with a model of the same general form as for the primary outcome (independent variables: treatment assignment (ID/LAB vs TAU), Site as a fixed effect, and baseline score as covariate where relevant) using logistic regression models (for binary outcomes), generalized linear model (for continuous outcomes), or longitudinal generalized mixed effects model (for longitudinal outcomes) with appropriate link functions (e.g. logit for binary outcomes). Longitudinal outcomes analyzed using a mixed effects models will utilize a generalized estimating equation with an autoregressive correlation structure (AR(1)) to account for within subject correlation over time, as well a random intercept accounting for between subject variability. In addition to site, covariates that are found to be related to the outcomes will be added to the models to improve the power for detecting significant differences.

Moderation and Mediation: Moderation Statistical Models: The effect of randomization to the ID/LAB vs TAU arms will be estimated for subpopulations based on the demographic and baseline characteristics selected as moderators (see above). We will estimate the moderation effect on primary outcome using a similar model to Aim 1 primary outcome with the inclusion of moderator by treatment interaction: $Y_i = \beta_0 + \beta_1 Trx_i + \beta_2 M_i + \beta_3 Trx_i M_i + \beta_4 C_i + s_i$ where M_i is the moderator status for i^{th} subject and Trx_i is subject's treatment assignment. Regardless of the significance of the interaction term, we will use the model to estimate the 95% confidence interval of the treatment effect for each level or category of the moderator variable, or the treatment effect at selected values of the moderator variable, if continuous. The moderator analyses are exploratory and hypothesis generating, but significant moderator effects can be useful in planning future efforts at implementation of medication treatment for opioid use disorder in medical settings by identifying subgroups that may particularly benefit. Identifying subgroups where there is less benefit may suggest future modifications to the implementation strategy to achieve better effect in those subgroups.

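### The ethnicity moderator model could carry about half of any site difference in treatment effect into the Hispanic and non-Hispanic estimates, because most Hispanic participants are expected at New Haven and no treatment-by-site term is planned

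*Combined protocol and SAP*

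**What the plan says.** **Expected ethnicity.** Section 5.0, under Eligibility Screening, gives for Hershey "Ethnically 1.5% Hispanic or Latino", for Greenville "Ethnically 7% Hispanic or Latino" and for New Haven "Ethnically 27% Hispanic or Latino". Section 6.0 plans 200 participants, "approximately 67 per site-region".

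**Moderators.** Section 12.0 (Additional variables) lists among the moderators "Demographic characteristics (gender, age, ethnicity, living situation (domiciled vs homeless". Site has three levels and enters every analysis as a fixed effect. It is not a listed moderator.

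**Model and reporting.** The moderation paragraph of Section 12.0 takes the primary-outcome model and adds the moderator and its product with treatment. No product of treatment and site appears. The equation's last term is not defined, but it is not multiplied by treatment either. The reporting rule covers every level of every moderator: "Regardless of the significance of the interaction term, we will use the model to estimate the 95% confidence interval of the treatment effect for each". The same paragraph calls these analyses exploratory, and says that subgroups with less benefit may suggest changes to the implementation strategy.

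**Usual care.** Section 7.0 says that usual care at Yale New Haven "ranges from Addiction medicine consultation with possible initiation onto MOUD, to no Addiction consultation followed by detoxification". For Greenville: "Current standard care for OUD is detoxification and consultation with a social worker who provides referral for care after discharge". Hershey and Waterbury are described as detoxification with outpatient referral. Bridgeport's usual care is not described. Section 10.0 leaves the start of medication in the TAU arm to the consulting team when a consultation takes place. Section 3.0 nevertheless expects the specified TAU to be fairly uniform across sites.

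**The concern.** The primary outcome is being on medication for OUD at 12 weeks. Where a consult service can start that medication in the TAU arm, TAU enrolment may be higher and the ID/LAB contrast smaller. A site main effect absorbs differences between sites in the level of the outcome. It does not absorb differences between sites in the treatment effect.

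Ethnicity and site are strongly associated in the planned sample. A site difference in treatment effect that has no term of its own will be picked up in part by the treatment-by-ethnicity term. The subgroup odds ratios are to be reported whatever the interaction test shows. A difference arising from local usual care could therefore be read as a difference in benefit between Hispanic and non-Hispanic patients.

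**Working it through.** **Planning figures.** The plan states no figure for this moderator. Its power statement reproduces: 100 per arm, 40% vs 59.7%, two-sided 5%, gives power 0.800, and the odds ratio is (0.597/0.403)/(0.40/0.60) = 2.22. The plan's 60% for ID/LAB is used below.

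**Step 1: concentration.** Inputs are the shares in Section 5.0 and 67 per region from Section 6.0. The New Haven share is assumed to hold for all Connecticut participants.

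| | Hershey | Greenville | New Haven | Total | New Haven share |
|---|---|---|---|---|---|
| Hispanic | 67 × 0.015 = 1.0 | 67 × 0.07 = 4.7 | 67 × 0.27 = 18.1 | 23.8 | 76.1% |
| Non-Hispanic | 66.0 | 62.3 | 48.9 | 177.2 | 27.6% |

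If New Haven supplied 50 or 100 of the 200, with the rest split equally, its share of Hispanic participants would be 68% or 86%.

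**Step 2: how much carries over.** With 1:1 allocation within site and no treatment-by-site term, the fraction of a New Haven vs other-site difference in effect that moves into the ethnicity interaction is about the difference in New Haven shares: 0.761 − 0.276 = 0.485. Logistic fits to expected counts give 0.48.

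**Step 3: size under assumed rates.** The documents give no site-specific rates, so the TAU rates here are assumptions. ID/LAB is 60% at every site and ethnicity has no effect within any site. The planned model (treatment, ethnicity, their product, site) is fitted to expected counts.

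| Assumed TAU, Hershey/Greenville/New Haven | Non-Hispanic OR | Hispanic OR | Ratio |
|---|---|---|---|
| 40/40/45% | 2.13 | 1.93 | 0.91 |
| 40/40/50% | 2.01 | 1.65 | 0.82 |
| 35/35/50% | 2.34 | 1.74 | 0.74 |
| 40/40/60% | 1.80 | 1.22 | 0.68 |
| 30/30/60% | 2.46 | 1.35 | 0.55 |

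The first row by hand: the site odds ratios are (0.60/0.40)/(0.40/0.60) = 2.25 and (0.60/0.40)/(0.45/0.55) = 1.83. Then ln(1.83/2.25) = −0.205, × 0.484 = −0.099, and exp(−0.099) = 0.91. The true ratio is 1.00 in every row. Adding treatment-by-site returns it to 1.00 in every row.

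**Step 4: precision.** The SE of the interaction (log scale) is about 0.89 in the planned model and 0.94 to 0.96 with treatment-by-site, which is 6-7% larger. Bias and added variance compare as follows.

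| Assumed TAU | Bias (log scale) | Squared bias | Added variance |
|---|---|---|---|
| 40/40/45% | −0.10 | 0.01 | 0.10 |
| 35/35/50% | −0.30 | 0.09 | 0.105 |
| 40/40/60% | −0.39 | 0.15 | 0.11 |
| 30/30/60% | −0.60 | 0.36 | 0.12 |

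A simulation of about 3,000 trials under 40/40/60% rejected the null for the interaction in about 6% of trials with the planned model and about 4% with treatment-by-site.

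**Step 5: where the information lies.** Once treatment-by-site is in the model, a site informs the ethnicity contrast roughly in proportion to 67 × share × (1 − share): 0.99, 4.36 and 13.21. New Haven holds 13.21/18.56 = 71%.

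**The case against.** Several points on the other side stand.

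- Section 7.0 describes existing hospital practice. The trial's TAU is specified in Sections 3.0 and 10.0: diagnosis, counselling, a recommendation to consider consultation, overdose education, Nurse Care Manager contact and referral for all. Section 3.0 expects this to be fairly uniform across sites. Section 10.0 still ties consultation to local availability, so a site difference is possible, but its size is unknown.
- New Haven practice extends down to detoxification without consultation, and Waterbury resembles Hershey. If Waterbury and Bridgeport are in the Connecticut stratum, the contrast is weaker. Section 5.0 gives no ethnicity figure for either.
- The analysis is labelled exploratory, and single-moderator models with site as a main effect are conventional. With about 24 Hispanic participants the intervals are very wide: under 35/35/50% the expected 95% interval is about 0.34 to 8.9 for the Hispanic odds ratio and 0.13 to 4.2 for the interaction ratio. Readers will see this.
- Under the milder assumptions the added variance exceeds the squared bias, so replacing the planned model would not clearly improve the estimate.

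What does not stand is that the exploratory label settles the matter. It warns of chance findings, not of a systematic shift in estimates that are reported regardless of the test.

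A reader might infer that any ethnicity difference this model reports is simply the site difference. The documents do not support that: they do not establish that treatment effects differ by site, and only about half of such a difference would carry over. Nor do they support a reading in which the primary result is biased, or in which false positive interaction tests become common.

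**Conclusion.** The point holds in conditional form. If the treatment effect differs between New Haven and the other sites, the planned ethnicity model would attribute about 48% of that difference (log odds ratio scale) to ethnicity. With no true ethnicity effect, the reported odds ratios would range from 2.13 vs 1.93 under a mild assumed site difference to 2.46 vs 1.35 under a strong one. The last case sets TAU equal to ID/LAB at New Haven and marks the far end of the range.

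This rests on the Section 5.0 share for New Haven applying to about 67 Connecticut participants, on roughly equal regional enrolment, and on assumed TAU rates. The primary analysis is unaffected. The matter is minor: it concerns how one exploratory subgroup estimate is read, and that estimate will be imprecise with either model.

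**What to change.** In the moderation paragraph of Section 12.0, add for the ethnicity moderator that a companion model with treatment-by-site terms (2 df) will be fitted and reported beside the planned model, with its ethnicity-specific effects averaged over the three sites using the same weights for both groups. State that about 18 of 24 Hispanic participants are expected at New Haven, so the ethnicity contrast rests mostly on comparisons within that site. Define the last term of the moderator equation at the same time.

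Keep the planned model. If the two models agree, the reader is reassured. If they diverge, the reader can see that site may be part of the explanation. The cost is a line or two of text, two model terms, and an interaction SE about 6-7% larger in the companion model. No data collection or sample size changes.

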8.0 Recruitment Methods

Patients eligible for the study will be admitted either through the emergency department or directly to the medical wards. The study team at each Site will conduct regular outreach to the staffs of these services to make them aware of the study and how to refer patients, and work with the attending physician to determine likely eligibility. In many cases, potentially eligible patients will be admitted to the ID or Hospitalist service that is conducting the study. Research assistants will conduct a daily chart review of the patient lists for the Infectious Diseases and Hospitalist teams via the electronic medical record to pre-screen for eligibility. In addition, informational study flyers will be distributed to the Infectious Disease, Addiction Medicine (if applicable) and hospitalist teams with the contact information of the project coordinator for referral of participants. Potentially eligible patients will be given a study information sheet and asked if they are interested in considering participation. It will be stressed that participation is voluntary and that those not interested will receive standard care for their medical problems and OUD--detoxification, opioid overdose

education, and recommendations and assistance with referral to community-based addiction treatment upon hospital discharge. Patients who express interest in learning more about the study will have a consent discussion with a member of the study team or one of the physicians working on the study, and provide written informed consent. Participants will complete a brief 'Consent Quiz' confirming comprehension. A member of the study team will then complete baseline assessments; medical evaluation for study medication treatment, safe study participation and eligibility confirmation. Eligible, interested participants will then be randomized.

A study information sheet will be created before recruitment begins and shared with each potential participant and will be used to recruit subjects. The brochure will explain why they are being recruited (because they are hospitalized for an infection), the purpose of the study, how the study may benefit them, and how study randomization works. The Yale Center for Clinical Investigation (YCCI)'s Recruitment and Marketing unit will assist Yale investigators in creating a brochure that is applicable to each study site.

